## 7.2 Estimated sample size, and estimated numbers of patients recruited at each study center, with supporting statistical information

This clinical randomized controlled superiority trial will seek to demonstrate that the D28 mortality rate in patients admitted to the ICU and treated with mechanical ventilation and vasoactive amines is lower in patients given early enteral nutrition than in patients given early parenteral nutrition. Assuming a 37% D28 mortality rate in the parenteral-nutrition group and a 5% decrease in mortality with early enteral nutrition (i.e., a D28 mortality rate of 32%), with the alpha risk set at 4.9% and the beta risk at 20%, 1427 patients are needed in each group (Newcombe, Statist Med 1998; 17:873-890), i.e., a theoretical total of 2854 patients.

The mortality rates used for the sample size estimation are those obtained in the NUTRIREA-1 randomized controlled trial in nine centers (CRICS network), in which similar inclusion criteria were used.

### Ancillary studies

#### *– Ancillary study 1*

The primary outcome measure is the plasma citrulline level at H72. To demonstrate a significant difference between plasma citrulline levels of 16  $\mu\text{moL/L}$  (enteral-nutrition group) and 12  $\mu\text{moL/L}$  (parenteral-nutrition group), with a standard deviation of 8  $\mu\text{moL/L}$ , a two-tailed test, the alpha risk set at 0.05, and 90% power, 85 patients will be needed in each group (170 patients in all).

#### *– Ancillary study 2*

The primary outcome measure is the proportion of patients with abundant microaspiration. We expect that the proportion of patients with abundant microaspiration will be 50% in the enteral-nutrition group and 30% in the parenteral-nutrition group. With the alpha risk set at 0.05, to obtain 80% power, 94 patients will be needed in each group (188 patients in all), with simple random sampling.

## 7.3 Degree of statistical significance planned for the study

The statistical tests will be performed using a significance threshold of 1% for the interim analyses and 4.9% for the final analysis.

## 7.4 Statistical rules for study discontinuation

We will perform two interim analyses, after inclusion of the first 1000 and the first 2000 patients, respectively. We will use Peto's boundary (*Peto R, Pike MC, Armitage P, et al. Design and analysis of randomized clinical trials requiring prolonged observation of each patient. I. Introduction and design. Br J Cancer 1976;34:585-612. PMID*):

- the significance level associated with the first interim analysis is 0.01;
- the significance level associated with the second interim analysis is 0.01;
- the significance level associated with the final analysis is 0.049.

This method yields an overall Type I error of 5%.

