#### 4.5.2 Discontinuation of all or part of the study

Given that this study investigates standard practice, no study discontinuation criteria have been defined in advance, except the following:

1. scientific publication resulting in a consensus that challenges the primary study hypothesis or the method used to treat mechanically ventilated patients;
2. interim analysis conducted by the independent data monitoring committee and showing an early significant difference in the primary endpoint .

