#### 7.1.3 Analysis of the primary endpoint

Day-28 mortality will be reported as the point estimate with the 95% confidence interval in each group. Day-28 mortality will be compared between the two groups using the chi-square test.

---

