## 7.6 Handling of changes to the initial statistical analysis plan

The statistical analysis plan will be finalized when the database is locked.

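### The significance levels 0.01, 0.01 and 0.049 give an overall Type I error of about 5.7%, not the 5% that section 7.4 states

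*Combined protocol and SAP*

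**What the plan says.** Section 7.4 fixes the looks: "We will perform two interim analyses, after inclusion of the first 1000 and the first 2000 patients, respectively". It names Peto's boundary and lists the levels: "the significance level associated with the first interim analysis is 0.01", the same level at the second interim, and 0.049 at the final analysis. It closes with "This method yields an overall Type I error of 5" per cent.

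Section 7.3 gives the same levels in percentages: "significance threshold of 1% for the interim analyses and 4.9% for the final analysis". Section 7.2 sizes the trial on the final level, "with the alpha risk set at 4.9% and the beta risk at 20" per cent, for 37% versus 32% day-28 mortality, and arrives at 1427 per group, 2854 in all.

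Section 7.1.3 names the primary test: "Day-28 mortality will be compared between the two groups using the chi-square test". Section 4.5.2 lists, as one of two reasons to discontinue the study, an "interim analysis conducted by the independent data monitoring committee and showing an early significant difference in the primary endpoint". No section says whether the levels for the main trial are one-sided or two-sided.

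**The concern.** A final test at 0.049 uses 4.9% by itself. To stay at 5% overall, the two interim looks may add no more than 0.1 percentage points: the probability, under no effect, of crossing at an interim without also crossing at the end. Two interim looks at 0.01 each looked far too generous for that.

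The rule governs the confirmatory mortality claim and decides whether a 2854-patient trial stops early. If the interim level was meant to be smaller than 0.01, an interim p-value between the two figures would stop the trial under one reading and not under the other. If 0.01 was meant, the final level is too high for the stated 5%.

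**Working it through.** **Inputs.** Levels 0.01, 0.01, 0.049 (7.3, 7.4). Looks at 1000 and 2000 patients (7.4) and 2854 (7.2). Information fractions: 1000/2854 = 0.350, 2000/2854 = 0.701, and 1. Mortality 37% versus 32%, 1427 per group (7.2).

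**Sidedness, from the plan's own sample size.** With mean mortality 0.345,

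n = [z_α·√(2·0.345·0.655) + z_0.80·√(0.37·0.63 + 0.32·0.68)]² / 0.05².

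- Two-sided 0.049 (z = 1.969): (1.969·0.6723 + 0.842·0.6713)² / 0.0025 = 1426.5, which rounds up to the stated 1427.
- One-sided 0.049 (z = 1.655): 1125.4, which does not match.

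The sample size therefore reproduces and implies two-sided levels.

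**Overall error.** Under no effect, the three standardized differences are jointly normal with correlation √(n_i/n_j) between looks i < j. The overall error is the probability that |Z| exceeds its critical value at one look or more. The critical values are 2.576, 2.576 and 1.969. Recursive numerical integration gives:

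| Look | Patients | Level | Error spent at this look | Cumulative |
|---|---|---|---|---|
| 1 | 1000 | 0.01 | 0.0100 | 0.0100 |
| 2 | 2000 | 0.01 | 0.0077 | 0.0177 |
| 3 | 2854 | 0.049 | 0.0394 | 0.0571 |

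The interim looks add 0.0571 − 0.049 = 0.0081 to the final test's own error. The stated total leaves room for 0.05 − 0.049 = 0.001.

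**Could another reading give 5%?** None of those tried does.

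| Reading | Overall error |
|---|---|
| One-sided levels | 0.0557 |
| Equally spaced looks | 0.0575 |
| Final level 0.05 | 0.0580 |
| Look at 1000 only | 0.0552 |
| Look at 2000 only | 0.0513 |
| Simulated chi-square tests, null mortality 34.5% or 37% | 0.057 to 0.058 |

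**What would give 5%.** With the final level at 0.049, equal interim levels can be at most 0.00185. With interim levels of 0.01, the final level can be at most 0.0413.

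**Operating characteristics under 37% versus 32%, 1427 per group.** The expected final Z is 0.05/√(0.4507/1427) = 2.81.

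| Levels | Overall error | Crossed at look 1 | Crossed by look 2 | Power |
|---|---|---|---|---|
| 0.01, 0.01, 0.049 (as written) | 0.0571 | 18% | 44% | 80.7% |
| 0.001, 0.001, 0.049 | 0.0495 | 5% | 19% | 80.1% |
| 0.00185, 0.00185, 0.049 | 0.0500 | 7% | 24% | 80.2% |
| 0.01, 0.01, 0.041 | 0.0497 | 18% | 44% | 78.7% |

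For the last row, the fixed-sample formula gives 77.8% power at 1427 per group and needs 1503.6, so 1504 per group, for 80%. Counting the interim looks, about 1473 per group suffices.

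**The case against.** The strongest reply is about size. The excess is 0.7 percentage points. The hypothesis is directional, and in that direction the chance of a false claim is about 2.85% (half of 5.7%) against a nominal 2.5%. The sample size is sound and power as written is slightly above 80%. All of that stands: the effect is small. It does not make the stated 5% true, because 5.7% does not round to 5%. Nor is an interim crossing remote, at 44% by the second look under the plan's own assumptions.

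A second reply is that the monitoring committee might treat a crossing as advice. Section 4.5.2 does not say that stopping is automatic, and if a crossing did not count as rejection the realized error would be lower. But 7.4 presents the levels as discontinuation rules and derives the overall error from them, so counting each crossing as rejection is the natural reading.

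A third is that the analysis plan is still open. Section 7.6 says "The statistical analysis plan will be finalized when the database is locked", which falls after both interim analyses and so is too late to settle the rule they use. That timing is not itself part of the arithmetic conflict.

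**Conclusion.** The point holds: the levels in 7.3 and 7.4 and the 5% in 7.4 are incompatible. As written, the overall two-sided Type I error is 5.7%, an excess of about 0.7 percentage points. Across sidedness, look spacing and method of calculation, with both interim looks and the stated levels kept, it runs from 5.6% to 5.8%. The figure assumes that each look uses the day-28 status of exactly 1000, 2000 and 2854 patients and that any crossing counts as rejection. Two-sided testing is inferred from the sample size, but the conclusion does not depend on it. The documents do not show whether the interim levels, the final level or the 5% statement is the error.

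**What to change.** The sponsor, with the data monitoring committee, should choose one repair before the first interim analysis and carry it through every section it touches.

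- **Option A: smaller interim levels.** Set both interim levels to 0.001 in 7.3 and 7.4 and keep 0.049. Overall error is 4.95%, and 7.2 stands at 1427 per group with about 80% power. The cost is harder early stopping: under the plan's effect, the chance of crossing by the second look falls from 44% to 19%. The value 0.001 is one choice; any equal interim level up to about 0.0018 holds 5%, and at that limit the chance is 24%.
- **Option B: smaller final level.** Keep 0.01 at the interims and set the final level to 0.041 in 7.3 and 7.4. In 7.2, replace alpha 4.9% with 4.1% and restate power at 1427 per group as about 79% (78% by the fixed-sample formula). Alternatively, restore 80% with about 1473 per group (2 × 46 = 92 more patients) counting the interim looks, or 1504 per group (2 × 77 = 154 more) by the fixed-sample formula. If N changes, recompute the final level for the new information fractions. Early stopping stays as planned.

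If neither is adopted, the sentence in 7.4 must at least give about 5.7%. That makes the text true but does not restore 5% control.

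In all cases, state in 7.3 that the levels are two-sided. Under section 11.2 the change goes to the ethics committee if it is classed as substantial.

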## 7.5 Handling of missing, unused, or invalid data

In this study, patients from whom consent to the study was not obtained and those who secondarily withdrew their consent will not be included in the analyses. Apart from these two situations, the likelihood that patients will be lost to follow-up is small. The study patients will be admitted to ICUs, and the primary endpoint is objective (D28 mortality). However, should there be any patients for whom information on the primary endpoint is missing, then these patients would be considered as having died before D28, in both randomized arms.

## 7.6 Handling of changes to the initial statistical analysis plan

The statistical analysis plan will be finalized when the database is locked.

## 7.7 Selection of patients to be included in the analyses

The analyses will be conducted using the intention-to-treat (ITT) approach.

# 8 RATIONALE FOR REQUESTING CATEGORIZATION OF THE TRIAL AS A STUDY OF STANDARD CARE

Given the characteristics of the research project, the chief investigator considers that this project is primarily a **study of standard care**, based on the following arguments:

---

- all the nutritional-support interventions and protocols will be performed according to standard ICU practice;
- the study consists in evaluating combinations of diagnostic and prophylactic interventions and medical strategies (nutrition administration and monitoring protocol, diagnosis of VAP) that are used in everyday practice, i.e., whose indications are defined by professional consensus;
- the study does not involve any techniques or strategies that are innovative or obsolete;
- the combination of interventions (enteral or parenteral nutrition) is not new;
- the study consists in comparing two medical strategies (enteral and parenteral nutrition) for which no available data indicate that one is better than the other in terms of safety or efficacy.

Indeed,

- international guidelines recommend a specific management strategy (prefer early enteral nutrition over parenteral nutrition)
- but this strategy is either not used at all or used improperly in a large number of patients, for the following reasons:
  1. it is in itself a source of potential complications, and concern about this risk and/or the need to manage the complications should they occur result in an increased workload and in delayed or absent use of early enteral nutrition;
  2. the available studies (metaanalyses) have produced conflicting results;
  3. and the authors of the recommendations acknowledge that their guidelines rest on converging data and indirect studies and not on sound evidence, most notably from randomized trials that are adequately powered and use relevant clinical objectives;
- the widely conflicting results of recent studies on early supplemental parenteral nutrition constitute indirect evidence that the issue remains unsettled.
- Finally, the specific modalities used in the study are expected to minimize risks (by increasing the stringency of the enteral and parenteral nutrition delivery protocols) and place only negligible constraints on study participants (Article R 1121-3 of the French Public Health Code [CSP], decree n° 2006-477, 26 April 2006).

The Poitiers Ouest III ethics committee (*Comité de Protection des Personnes de Poitiers Ouest III*) has categorized the NUTRIREA-II trial as a study of standard care and has approved the conduct of the NUTRIREA-II trial (approval date, 26 January 2012, see letter enclosed).

---

## 9 RIGHT OF ACCESS TO THE STUDY DATA AND SOURCE DOCUMENTS

### 9.1 Access to the study data

The medical data about each patient will be communicated only to the institution with which the chief investigator is affiliated or to a person appointed by the chief investigator under conditions that ensure the confidentiality of the patient data.

### 9.2 Source documents

If needed, the institution to which the chief investigator is affiliated may request direct access to the medical record to check the study procedures and/or data, without violating confidentiality rules and within the limits set by laws and regulations.

### 9.3 Data confidentiality

Individuals having direct access to the study data will take all the necessary precautions to ensure the confidentiality of the data pertaining to the study participants, most notably regarding their identity and the results obtained during the study.

These individuals, together with the study investigators, are under an obligation to maintain confidentiality (under the conditions defined in articles 226-13 and 226-14 of the French penal code). During or at completion of the study, the data collected from the study participants and communicated by the individuals involved in the study will be rendered anonymous.

Under no circumstances will the names or addresses of the study participants be included in the study data.

Only the first letter of the last name and the first letter of the first name of each patient will be recorded, and these letters will be combined with a number to form a study-specific identifier reflecting the order of patient inclusion.

---

## 10 QUALITY ASSURANCE

To optimize the conduct of the study, a Clinical Research Assistant (CRA) will be in charge of performing the following tasks:

- preparation of the file to be submitted to the ethics committee (*Comité de Protection des Personnes*, CPP) and of the files for the CCTIRS and CNIL;
- finalization of the study documents (e.g., case-report form) and communications among individuals involved in conducting the study;
- study initiation in the study centers;
- verification of the data collected for the study;
- and documentation, registering, and reporting of the study data, in compliance with Standard Operating Procedures.

## 11 ETHICAL EVALUATION OF THE SPECIFIC MONITORING MODALITIES DEFINED IN THE RESEARCH PROTOCOL

### 11.1 Ethics committee (Comité de Protection des Personnes, CPP)

This research protocol and the patient information and consent documents have been submitted to the Poitiers CPP, which categorized the trial as a study of standard care and approved the conduct of the trial (approval date, 26 January 2012, see letter enclosed).

### 11.2 Substantial modifications

Any substantial modification to the study protocol will be communicated to the ethics committee (CPP) to ensure that the suggested modifications have no adverse effect whatsoever on the protection afforded to the study participants.

### 11.3 Patient information sheet and informed consent form

The patients will receive full and honest information, delivered in understandable terms, about the study objectives and their right to refuse to participate in the study or to withdraw from the study at any time. This information will be given in a patient information and

---

informed consent document, which will be handed to each patient. An information document dealing specifically with the ancillary studies will also be given to each patient.

---

## **12 HANDLING OF THE STUDY DATA AND STORAGE OF THE STUDY DOCUMENTS AND DATA**

### **12.1 Case-report form**

An Internet-based data collection tool will be used for this study. This electronic case-report form will be available at each of the study centers. Access to the electronic case-report form will require only an Internet connection and a browser. A document explaining how to use the electronic case-report form will be given to the study investigators.

Tests designed to check data consistency will be performed as an integral part of the electronic format. The electronic case-report form has an audit function that tracks any modifications made to the study data. The audit function also clearly identifies the person who made the modification, as well as the date. The reason for the modification can be supplied as a comment if deemed appropriate.

### **12.2 Data entry and analysis**

The data will be entered into an electronic case-report form via an Internet browser. The data will be analyzed by a biostatistician at the CIC INSERM202, under the responsibility of [name].

### **12.3 French Data Protection Authority (CNIL)**

Approval of the data handling procedure required for the study will be sought from the French Advisory Committee on Data Handling in Healthcare Research (CCTIRS) and, subsequently, permission will be requested from the French Data Protection Authority (CNIL) regarding the handling of personal data with the goal of conducting research on standard care.

---

## **13 FUNDING AND INSURANCE**

---

### 13.1 Study budget

Since this study will investigate standard care, the medical interventions will not require special funding. The expected total duration of the study is 3 years (30 months for patient inclusion and 6 months for follow-up and data verification) for 28 centers. The study will therefore require the following financial resources:

- CRA time for
  - study monitoring and coordination (10% of a full-time salary, for 3 years): 14 265 €;
  - monitoring visits (study initiation and completion visits, four 2-day visits /year/center, i.e., two full-time ARC salaries for 3 years): 285 300 €
- Clinical research technician (CRT) or clinical research nurse (CRN) time in each study center to assist in preparing and implementing the electronic case-report form and in study coordination and logistics, and to enter data into the electronic case-report form (4 to 5 h minimum/patient, i.e., for a mean of 102 patients included in each study center, 10% of a full-time salary/year for 3 years): 376 320 €
- Data handling:
  - Data management time to create the electronic case-report form and to monitor data quality (20% of a full-time salary the first year and 7% for each of the next 2 years): 15 096 €
  - Statistical analysis (1 month full-time, during the last year): 5000 €
- Meetings, coordinator missions (three 1-day-long meetings/3 years – 2 representatives/center for 28 centers; mean cost of 100 € per trip): 16 800 €
- Travel expenses for on-site study initiation, monitoring, and study completion visits (4.5 visits per an and per center on average, i.e., 378 visits each lasting 2 days, with a mean cost of 200 €): 75 600 €
- Stationery for the patient information and consent documents to be given to the patients or next of kin, bedside nutrition monitoring charts: 5100 €
- Study report costs (translation and submission: 2000 €) and costs of study result presentation at one national meeting (1000 €) and one international meeting (2000 €): 5000 €

Total budget: 798 481 € (not counting operating expenses estimated at 10%)

---

## 13.2 Insurance

The ethics committee has categorized the trial as a study of standard care, thus indicating that study participation involves no additional risks to the patients, and consequently the insurance held by the facilities delivering medical care to the study patients will cover the activities of the study (article L.1142-2 of the French Public Health Code).

---

## 14 STUDY FEASIBILITY

The study will be conducted in the 28 study centers, which include centers belonging to the Clinical Research in Intensive Care and Sepsis (CRICS) network. The feasibility of the NUTRIREA-2 trial was assessed based on the results of the NUTRIREA-1 trial, in which nine CRICS network centers participated during the 8-month study inclusion period. In all, 1736 patients were evaluated for study eligibility and 452 were included. In this population, 239 patients received vasoactive amine therapy. After the exclusion of two centers where previous organizational difficulties – now resolved – resulted in the inclusion of only very few patients, the mean number of patients included per month and per center was 4.3. These data establish the feasibility of NUTRIREA-2 with 28 participating centers and an inclusion period of 30 months at the most.

[figure not shown]
## 15 PUBLICATION POLICY

[figure not shown]
Communications and scientific reports relevant to this study will be under the responsibility of the chief investigator, who will obtain the approval of the other investigators. The co-authors of the study report and publications will be the investigators and clinicians involved in the study, in proportion to their contributions to the study, together with the biostatistician and associated investigators.

The publication policy will comply with international recommendations (N Engl J Med, 1997; 336:309-315).

